## **B.** Inflammatory Bowel Disease

- o IBD severity at time point post-FMT
  - Quiescent, mild, moderate, severe
  - Disease activity scores (if available)
- o IBD related hospitalizations post-FMT
- IBD surgeries post-FMT
  - Number of days or weeks post-FMT
- IBD-related medications post-FMT
  - Antibiotics
    - IV
    - Oral
  - Probiotics
  - Diet
    - Type of diet
  - Mesalamine
    - Oral
    - Rectal
  - Thiopurines
  - Methotrexate

- Steroids
  - Oral
  - Rectal
  - IV
- Biologics
  - Anti-TNF
  - Anti-Integrin
  - Other
- Cyclosporin or tacrolimus
- Other
- Other complications
  - Reclassification of disease type
  - Change in disease distribution
  - Abscess
  - Fistula
  - Perforation

## Supplement 5. FMT Short-term Adverse Outcomes (within 30 days)

- Procedure-related
  - Sedation complication
  - Bleeding
  - Perforation
  - o Other
- Symptoms post-FMT (within 30 days)
  - Diarrhea
  - Constipation
  - Nausea and/or vomiting
  - o Bloating
  - Abdominal pain
  - o Fever
  - Headache
  - Rash
  - Weight gain or loss
  - Other\_\_\_
- Surgeries or other Procedures
  - Describe
- Documented Infection (any)
  - Specify site/organism
  - o FMT related (related, possibly related, unrelated)
- Hospitalization
  - o Reason for hospitalization
  - o FMT related (related, possibly related, unrelated)
- Life-threatening experience
  - Describe/diagnosis
  - o FMT related (related, possibly related, unrelated)
- Death
  - Cause of death
  - o FMT related (related, possibly related, unrelated)
  - o Site of death
    - Hospital
    - Home
    - Convalescent or skilled nursing facility

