## 2.2 Rationale for Study Objectives Measures

## 2.2.1 To assess short-term and long-term safety

The safety of FMT is currently the greatest concern related to its use, and characterizing the safety of FMT and subsequent gut-related-microbiota products is the primary goal of the Registry. Short-term adverse events (AEs) relate primarily to the method of delivery (e.g., colonoscopy) and to acute infections or other adverse events from the donor fecal material and should be readily definable and quantifiable. Of greater concern and uncertainty is the possibility of long-term AEs. The human-to-human transfer of feces may be associated with long-term health risks to the recipient because the gut microbiota is composed of many components that have not been characterized and can change over time in ways that cannot be currently predicted. It is imperative to determine if FMT leads to unintended development of serious conditions due to the transfer of gut microbiota. In addition to infections, the possibility that gut microbiota associated with a disease phenotype (e.g., obesity, diabetes, cardiovascular disease) will be transplanted and result in chronic disease in recipients must be assessed. A prospective registry in a large sample of patients with long-term follow-up is the only practical method to achieve this aim at present.

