## 8 Statistical Plan

## 8.1 Sample Size Determination and Power

As noted in the AHRQ's Registry User's Guide, registries are used to provide precise estimates of outcomes in real-world practice and document that potential adverse events occur at less than a pre-specified incidence with a predefined level of confidence. Plans for the FMT registry include a sample size of approximately 4,000 patients, which will provide precise estimates of incidence rates for common and rare events. For example, if the incidence of an outcome after FMT in the Registry population is 5.0%, the 95% CI will be 4.4% to 5.7%, indicating a precise estimate of treatment effect. The planned sample size will also provide high confidence in ruling out rare adverse events. If an adverse event does not occur in the planned population of 4000 patients, we will have 95% confidence that the adverse event occurs at a rate of less than one in a thousand patients undergoing FMT.

The FMT registry also will support comparative effectiveness studies focusing on different methods of delivery of FMT (e.g., colonoscopy, enema, upper GI endoscopy, nasogastric or nasointestinal tube). Statistical power for comparative effectiveness studies will depend upon the incidence of the outcome and the distribution of use of the different methods of delivering FMT. For example, assuming an outcome that occurs in one out of 1,000 FMT procedures using one delivery method, there would be 90% power to detect a difference between an incidence of 0.001 and 0.008 assuming that 2,000 patients were exposed to each of the two delivery methods. For more common outcomes, the statistical power for specific relative risk estimate is greater. For example, with 2,000 patients in each group there would be 90% power to detect a difference between two approaches for which the incidence rates of events were 3% and 5% (i.e., RR=1.67).

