## 8.3 Statistical Methods

The registry will be designed in a manner that will facilitate statistical analyses for the purpose of signal detection, generation of descriptive data, and the conduct of comparative effectiveness studies. There will be several major advantages of the registry design as opposed to a system of spontaneous reporting. Most importantly, a prospective cohort of patients who undergo FMT with collection of predefined outcomes will allow accurate estimation of incidence rates. In contrast, systems that rely on spontaneous reporting have incomplete numerator data and lack denominator data. The ability to calculate incidence rates greatly facilitates both descriptive epidemiology and signal detection.

As noted above, registries are used to provide precise estimates of outcomes in real-world practice and document that potential adverse events occur at less than a pre-specified incidence with a predefined level of confidence. Thus, descriptive statistics with 95% confidence intervals will be determined for the safety and effectiveness outcomes to provide precise estimates of incidences. As mentioned above, if an adverse event does not occur in the planned population of 4,000 patients, we will have 95% confidence that the adverse event occurs at a rate of less than one in a thousand patients undergoing FMT.

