## E. Method of delivery

- Oral ingestion: capsule
  - o Fresh capsule
  - o Frozen capsule
  - o Lyophilized capsule
  - o Number of capsules used
- Oral ingestion: liquid
- Nasogastric tube
- Naso-intestinal tube
- Upper endoscopy
- Sigmoidoscopy
- Colonoscopy
- Enema

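### The procedure-related block of the 30-day form names no harm particular to tube, enema or swallowed delivery, so comparing routes on procedural harm risks uneven capture

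*Protocol*

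**What the plan says.** Safety is the primary objective (Section 2.1). Section 2.2.1 states: "Short-term adverse events (AEs) relate primarily to the method of delivery (e.g., colonoscopy"). The same sentence goes on to name acute infections and other events arising from the donor material.

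Supplement 1 E lists eight delivery methods. Five are non-endoscopic: "Oral ingestion: capsule", oral liquid, nasogastric tube, "Naso-intestinal tube" and enema.

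In Supplement 5 the procedure-related block contains "Sedation complication", bleeding, perforation and 'Other', with no relatedness field. The rest of the form prompts, for every recipient:

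- symptoms, including "Nausea and/or vomiting", abdominal pain and fever;
- surgeries or other procedures;
- an item beginning "Documented Infection (any", with site and organism;
- hospitalization, life-threatening experience and death.

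Infection, hospitalization, life-threatening experience and death each carry a three-level FMT-relatedness field. Section 6.4 adds that spontaneous events are recorded too.

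Section 8.1 says the registry will support "comparative effectiveness studies focusing on different methods of delivery of FMT", and Section 8.3 repeats this. Neither section fixes the outcome to be compared. Section 8.3 argues for predefined outcomes on the ground that "systems that rely on spontaneous reporting have incomplete numerator data and lack denominator data".

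**The concern.** A harm with its own tick box is normally recorded more completely than one the site must think of and write in. The named procedural harms suit a sedated endoscopy best. A misplaced tube, a local tube injury, aspiration without a documented infection, a failed swallow or an anorectal injury from an enema has no item in that block. The expected-event list in Section 6.2.2 repeats the same three procedural items and also names no tube, enema or swallowing harm.

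If routes are then compared on procedure-related events, completeness of recording differs by exposure. The regression, propensity-score and risk-score methods in Section 8.3 adjust for differences between recipients. They cannot restore events that were never entered, and neither can a later analysis plan.

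**Working it through.** **1. What the form prompts, by type of harm**

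| Harm | Prompted in Supplement 5? |
|---|---|
| Sedation complication | Yes; close to endoscopy-specific |
| Bleeding, perforation | Yes; not tied to a route |
| Vomiting, abdominal pain, fever | Yes, all routes |
| Any infection, hospitalization, life-threatening event, death | Yes, all routes, with relatedness |
| Tube misplacement or injury, failed swallowing, anorectal injury, aspiration without documented infection | No named item; 'Other' only |

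The unprompted part is therefore a share of procedural harm, not all of it.

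**2. The plan's own power figures (Section 8.1)**

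Inputs: 2,000 patients per route; 0.001 v 0.008 and 3% v 5%; stated power 90% each. Alpha is not stated for these figures, so 0.05 two-sided is assumed.

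Power = Φ{(|p1 − p2| − 1.96·SE0)/SE1}, where SE0 = √[2·p̄(1 − p̄)/n] and SE1 = √[(p1(1 − p1) + p2(1 − p2))/n].

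- 3% v 5%: SE0 = √(2 × 0.04 × 0.96/2000) = 0.00620; SE1 = √((0.0291 + 0.0475)/2000) = 0.00619; (0.02 − 1.96 × 0.00620)/0.00619 ≈ 1.27, so power is 89.8%.
- 0.001 v 0.008: the same formula gives 91.1%.

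Both agree with the stated 90%.

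**3. Effect of uneven prompting**

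Let p be the true rate of the compared outcome on the non-endoscopic route, s the share of its events that no prompt covers, and c the capture of those events through 'Other' relative to a prompted item. Then

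recorded rate = p × [1 − s(1 − c)].

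The documents give neither s nor c, so the values below are assumptions chosen to show a range. The endoscopic route is taken as fully prompted. Any unprompted share on that side would shrink the difference.

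(a) True rates equal at 5%, 2,000 per route:

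| s | c | Recorded rate | Recorded RR | Chance of a result falsely favouring the non-endoscopic route |
|---|---|---|---|---|
| 0.10 | 0.7 | 5% × 0.97 = 4.85% | 0.97 | about 4% |
| 0.25 | 0.5 | 5% × 0.875 = 4.375% | 0.875 | 15% |
| 0.50 | 0.5 | 5% × 0.75 = 3.75% | 0.75 | 49% |

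The nominal chance in that direction is 2.5%.

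(b) True 3% endoscopic v 5% non-endoscopic (true RR 1.67, power 89.8%):

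| s | c | Recorded RR | Power |
|---|---|---|---|
| 0.10 | 0.7 | 4.85/3 = 1.62 | 85% |
| 0.25 | 0.5 | 4.375/3 = 1.46 | 64% |
| 0.50 | 0.5 | 3.75/3 = 1.25 | 26% |

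**4. When the mechanism is absent**

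If the compared outcome is prompted for every route (infection, hospitalization, death, CDI cure), s = 0 and the recorded rate equals p. If all routes are prompted alike, c = 1 and power returns to 91.1% and 89.8%. No figure stated in the protocol changes.

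**The case against.** The case against is substantial, and most of it stands.

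- Bleeding and perforation are not tied to endoscopy, and serious consequences of any route are prompted elsewhere on the form. A serious tube event judged related and absent from the Section 6.2.2 list could also be treated as unexpected and reported promptly under Section 6.4.
- Section 2.2.1 attributes short-term events to donor material as well as to delivery, and that half is prompted equally for all routes.
- Section 8.3's criticism concerns systems with no denominator. This registry follows a defined cohort and completes a form at 1 month, so only the point about incomplete numerators carries over.
- Section 5.1 describes the supplements as elements that may be collected, and the operative electronic form is not shown.
- Aspiration is not peculiar to tubes or swallowing. On general reasoning it can also follow sedation or upper endoscopy, which is a reason to ask every recipient.

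A reader might infer that the form suits endoscopy only and that the route comparison is biased as planned. The documents do not support this: they fix no outcome for that comparison, and the 3% v 5% figures are an illustration, not a target.

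A reader might also treat all non-endoscopic procedural harm as unprompted. With a true 1% rate, 90% capture when prompted and 30% when not, that gives 2,000 × 0.01 × 0.9 = 18 against 2,000 × 0.01 × 0.3 = 6, a false ratio of 3.0. It requires s = 1, which Supplement 5 contradicts, and capture rates found nowhere in the protocol.

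None of these arguments puts a tube, enema or swallowing item into the procedure-related block.

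**Conclusion.** The point holds in a limited, conditional form. Five non-endoscopic routes are in scope, and the procedure-related block names no harm particular to any of them. The loss is mainly of milder or purely procedural events and of their attribution to the procedure. If routes are compared on procedure-related events, there is a risk of differential ascertainment favouring the non-endoscopic routes.

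Its size cannot be determined from the protocol. Under the assumed shares and capture rates, with equal true rates of 5%, the recorded RR lies between about 0.97 (negligible) and 0.75 (material). Effectiveness outcomes and harms prompted for every route are unaffected. This is a worthwhile, inexpensive improvement to data collection for the primary safety objective. It is not evidence that any planned result is invalid.

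**What to change.** In the procedure-related block of Supplement 5, add yes/no items for harms of tube, enema and swallowed delivery, for example aspiration, tube misplacement or injury, failed swallowing and anorectal injury. Ask them of every recipient whatever the route. Give them the related / possibly related / unrelated field already used for infection and hospitalization; the block has no such field now, so it must be added.

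In Section 8.3, state that route comparisons of procedural harm use only items prompted for all routes, and that 'Other' entries are reported descriptively.

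The cost is a slightly longer 30-day form. No visit or procedure is added, and the power figures in Section 8.1 are unchanged.

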# **Supplement 3. FMT Treatment Indications and Baseline Donor/Recipient Characteristics**

#### A. FMT Indication

- C. difficile
  - Refractory
  - o Recurrent
  - Severe
- Inflammatory Bowel Disease
  - Ulcerative colitis
  - o Crohn's disease
  - o IBD-U
  - o Pouchitis
- Irritable bowel syndrome
  - o IBS-D
  - o IBS-C
  - IBS-M
  - o Other functional disorder
- Chronic constipation
- Obesity
- Diabetes
- Metabolic syndrome
- NAFLD/NASH
- Neurologic or Neurodevelopmental disorder
- Other

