## B. Baseline Characteristics

- Donor (if known)
  - o Age
  - o Race/Ethnicity
  - o Gender
  - o Height
  - Weight
  - Donor medical conditions (check any which apply)
    - No significant medical or surgical history
    - BMI ≥30
    - Hypertension
    - Hyperlipidemia
    - Diabetes type II
    - Depression/anxiety
    - CAD
    - Cerebrovascular disease
    - Asthma
    - Other\_\_\_
- Recipient characteristics (baseline)
  - o Age
  - o Race/Ethnicity
  - Gender

- Height
- Weight
- Medical co-morbidities
  - Metabolic (hypertension, diabetes II, hyperlipidemia)
  - Autoimmune (hypothyroid, RA, SLE)
  - Asthma/Allergic-Atopic conditions
  - Cardiovascular
  - Neurological conditions (MS, Parkinson, Alzheimer's, autism)
  - Psychological (depression, anxiety, eating disorder)
  - IBS
  - IBD
  - Immunocompromised from medical condition or medication
  - Other
- Labs (glucose, cholesterol, HDL, LDL, triglycerides, ALT, alkaline phosphatase, bilirubin, albumin, BUN, creatinine)
- CDI baseline characteristics
  - Disease characteristics (pre-FMT)
    - Mild illness (recurrent)
    - Moderate (more severe but uncomplicated disease)
    - Severe
    - Severe complicated
  - Duration of *C. difficile* infection (weeks between initial diagnosis and FMT)
  - Number of CDI episodes
  - C. difficile strain
    - o Nap-1
    - Non Nap-A
    - o Unknown
  - Other treatments courses received (and number of courses of each, if known) for CDI prior to FMT
    - o Metronidazole
    - o Vancomycyin
    - o Vancomycin taper/pulse dose
    - o Fidaxomicin
    - o Nitazoxanide
    - o Rifaximin
    - o IVIG
    - o Saccharomyces. boulardii
    - o Lactobacillus GG
    - Other probiotic
    - o Other\_\_
  - Immediate Pre-FMT treatment(s)
    - Antisecretory therapy?
      - No
      - Yes
- H2 blocker
- Proton Pump inhibotor
- o Probiotics?
  - No
  - Yes

- list
- Antibiotics?
  - No
  - Yes
- Metronidazole
- Vancomycin
- Other
- o If yes, were antibiotics stopped? (yes/no)
- Number of days off antibiotics prior to FMT
- IBD Baseline characteristics
  - o Type of IBD
    - CD
    - UC
    - IBD-U
    - Pouchitis
  - Disease location/extent
    - Montreal classification for adults >18 y/o
    - Paris classification for children <18 y/o

  - IBD treatment pre-FMT
    - Antibiotics
      - IV
      - Oral
    - Probiotics
    - Diet
      - Type of diet
    - Mesalamine
      - Oral
      - Rectal
    - Thiopurines
    - Methotrexate
    - Steroids
      - Oral

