      - Rectal
      - IV
    - Biologics
      - Anti-TNF
      - Anti-Integrin
      - Ustekinumab
      - Other
    - Cyclosporin or tacrolimus
    - Other
  - IBD history
    - Number of years since initial diagnosis
    - Bowel surgery (ever)
    - IBD-related hospitalizations (within 12 months prior to FMT)
  - Severity of IBD at time of FMT (quiescent, mild, moderate, severe)
  - Disease activity scores (if available)

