## **Supplement 4. FMT Effectiveness Outcomes**

## A. Clostridium Difficile Infection

- Post-FMT treatment(s)
  - o Probiotics?
    - No
    - Yes
      - list
  - Antibiotics?
    - No
    - Yes
      - Metronidazole
      - Vancomycin
      - Fidaxomicin
      - Other
  - Days post-FMT antibiotic stopped
- Cure (Resolution of diarrhea without need for further anti-CDI therapy)
  - Cured with single FMT
  - Cured with >1 FMT
- Failure/Recurrence
  - o How recurrence was diagnosed
    - Symptoms only
    - Stool testing only
    - Symptoms and +stool testing (EIA)
    - Symptoms and + stool testing (PCR)
  - Time of recurrence (weeks post-FMT)
- Antibiotics received post-FMT for treatment of other infections
  - Agent
  - o Indication
  - Months post-FMT

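### Supplement 5 lists 30-day symptoms without asking whether they are new or worse, and Supplement 3 records no symptom-level baseline, so the planned incidences mix persisting disease with new events

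*Protocol*

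**What the plan says.** Supplement 5 is the protocol's list of short-term adverse outcomes. Its symptom block, "Symptoms post-FMT (within 30 days", names diarrhea, constipation, nausea or vomiting, bloating, abdominal pain, fever, headache, rash and weight change. No item carries a qualifier for change from the pre-FMT state. The field "FMT related (related, possibly related, unrelated" is attached to infection, hospitalization, life-threatening experience and death, but not to symptoms. Section 6.2.1 asks for relatedness for SAEs only.

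At baseline, Supplement 3 A records the indication, which may be CDI, IBD, an IBS subtype or "Chronic constipation". Supplement 3 B records comorbidities, weight and laboratory values. For CDI it adds a severity class under "Disease characteristics (pre-FMT", plus history and prior treatment. For IBD it adds "Severity of IBD at time of FMT (quiescent, mild, moderate, severe" and "Disease activity scores (if available". It has no field for any of the individual symptoms above.

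Supplement 4 A defines the CDI endpoint as "Cure (Resolution of diarrhea without need for further anti-CDI therapy" and records failure or recurrence, how it was diagnosed and its time in weeks. Supplement 4 B repeats the four-level IBD severity scale after FMT. No other indication has a section in Supplement 4.

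Section 8.3 plans incidences with 95% confidence intervals for the safety outcomes, and intends the registry for signal detection and for comparing delivery methods.

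**The concern.** The listed symptoms are also features of the diseases being treated. Section 6.2.2 itself names diarrhea, constipation, abdominal pain and fever among events associated with FMT, CDI or IBD, without dividing them. A patient with IBS-D whose bowel habit has not changed enters the diarrhea count in the same way as a patient who develops diarrhea because of the procedure.

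Safety is the primary objective, and section 2.2.1 says that short-term events "should be readily definable and quantifiable". That is reasonable for a perforation or a documented infection. It does not hold for a symptom with no reference point. Two things are at stake. The reported incidence of the common symptoms may largely describe disease that persisted. And where delivery methods differ in effectiveness or in case mix, the less effective one will tend to look less safe.

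**Working it through.** **1. Reproduce the protocol's precision figure.** Section 8.1 gives 4.4% to 5.7% for a 5.0% incidence in 4,000 patients. With 200/4,000 the Wilson interval is 4.37% to 5.72%, which agrees. The half-width is about 0.7 percentage points and covers sampling error only.

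**2. Set the forms side by side.**

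| Group | Baseline item (Supplement 3) | Outcome item (Supplement 4) | Can persisting and new symptoms be told apart? |
|---|---|---|---|
| CDI, diarrhea | Severity class; pre-FMT antibiotics and days off them | Cure, failure or recurrence, weeks to recurrence | Largely |
| CDI, other symptoms | Severity class only | None | No |
| IBD, overall activity | Four-level severity; scores if available | Same scale and scores | Yes, globally |
| IBD, individual symptoms | None | None | No |
| IBS, chronic constipation, other indications | Diagnosis or subtype | None | No |
| Weight change, any indication | Weight | Not needed | Yes |

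**3. Illustrate the size.** Let f be the share of patients with persistent diarrhea and t the rate of new diarrhea among the rest. The protocol gives neither, so both are assumptions. The 11% row takes 100% − 89%, the mean cure rate quoted in section 1.2.

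Recorded incidence = f + (1 − f)t. Genuinely new = (1 − f)t. Persistent share = f / recorded.

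| f | t | Recorded | Genuinely new | Persistent share |
|---|---|---|---|---|
| 5% | 1% | 5.95% | 0.95% | 84% |
| 5% | 5% | 9.75% | 4.75% | 51% |
| 11% | 1% | 11.89% | 0.89% | 93% |
| 11% | 5% | 15.45% | 4.45% | 71% |
| 20% | 1% | 20.8% | 0.8% | 96% |
| 20% | 5% | 24.0% | 4.0% | 83% |

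In every row the excess of recorded over genuinely new is f itself, 5 to 20 points, against a half-width of about 0.7 points.

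**4. Comparison of two delivery methods.** Take t = 5% in both groups, 2,000 patients each, two-sided 5% level.
- f = 9% and 11%: recorded 0.09 + 0.91 × 0.05 = 13.55% and 0.11 + 0.89 × 0.05 = 15.45%. The chance of a significant difference is about 40%.
- f = 10% and 15%: recorded 14.5% and 19.25%. The chance is about 98%.

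New diarrhea among patients without persistent diarrhea occurs at the same rate in both groups. These values of f are also assumed, so the example shows the direction and mechanism of the bias and does not predict its size.

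**The case against.** Several points on the other side stand.

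- **The quantified case is the one best covered.** Diarrhea in a CDI patient recorded as a failure can be flagged with the Supplement 4 fields already listed. That is an analysis rule, and the SAP, which is not shown, may contain it.
- **Baseline disease status is recorded.** Indication, IBS subtype, CDI severity class and IBD severity give a partial picture, and IBD severity is repeated after FMT.
- **Broad capture is defensible.** Section 6.1 says the fields are meant to capture outcomes broadly, as possible indicators of a safety concern. For signal detection it is reasonable to record events without attributing them.
- **The supplements are not the case report form.** Section 5.1 presents them as elements that may be collected, so the form could hold more.

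A reader might infer that the protocol scores persisting disease as harm caused by FMT. The text does not say that. It counts symptoms as adverse outcomes without assigning a cause, and for SAEs section 6.2.1 includes the disease under treatment among the factors to weigh.

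A reader might also take 11% of 4,000, or 440 patients, as the expected number of false diarrhea events. That would need every patient to have CDI and every non-cure to show as diarrhea within 30 days. The registry admits many indications. Supplement 4 allows failure by stool testing alone and times recurrence in weeks, so it may fall after day 30. The 89% has no stated time window.

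The objections do not close the gap for individual symptoms. A SAP can add a counting rule, but it cannot supply a pre-FMT symptom that was not collected.

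**Conclusion.** The point holds in a limited form. As the protocol specifies data collection, the 30-day incidences of diarrhea, constipation, nausea or vomiting, bloating, abdominal pain and fever will combine persisting disease with new events. For CDI diarrhea the overlap can largely be separated with fields already planned, and IBD has a global comparison before and after FMT. The part that cannot be recovered is item-level: all of these symptoms in IBS, chronic constipation and other indications without a Supplement 4 outcome, and the non-diarrhea symptoms in CDI and IBD.

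The protocol gives no indication mix and no baseline symptom rates, so the unrecoverable part cannot be sized. The range of about 6% to 24% recorded, with 51% to 96% of it persistent, rests on assumed values of f and t for diarrhea. It shows only that the bias can far exceed the sampling error that section 8.1 describes as precise. This is a cheap improvement to the primary safety data, worth making before enrollment because the missing baseline cannot be added later.

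**What to change.** 1. Add the Supplement 5 symptom list to the recipient baseline form in Supplement 3 B.
2. On the 1-month form, record each symptom as absent, present but unchanged or improved, new, or worse than before FMT.
3. Keep reporting all symptoms, but use new-or-worse symptoms as the short-term adverse-outcome incidence.
4. Flag diarrhea in patients recorded as CDI failure or recurrence in Supplement 4. Report it under effectiveness and show it separately in the safety tables.

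Item 4 is needed alongside items 1 and 2. If antibiotics had suppressed CDI diarrhea before FMT, the symptom would be absent at baseline and a recurrence would be classed as new. The pre-FMT antibiotic fields in Supplement 3 B help to identify these patients.

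The cost is a short baseline checklist, a changed response option on one form and a few minutes of extra site data entry per patient.
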